Inclusion criteria: we will enroll 35-65 years old severely obese (BMI \geq or above 35 kg/m²) male veterans with hypogonadotropic hypogonadism defined as low total testosterone (lower than 300 ng/dl) taken from the average of two morning blood samples obtained between 8:00 and 11:00 AM in different days, at least 2-3 days apart, with LH lower than 9 U/L, estradiol above 40 pmol/l, and normal FT4, TSH, prolactin, cortisol, ACTH and IGF1 levels. Subjects must be ambulatory, willing and able to provide written informed consent.

Exclusion Criteria:

Exclusion criteria:

1) clinical or biochemical evidence of pituitary or hypothalamic disease; 2) any ongoing illness that, in the opinion of the investigator, could prevent the subject from completing the study; 3) any medication known to affect gonadal hormone levels, steroid hormone-binding globulin levels or bone metabolism (e.g., androgens, estrogens, glucocorticoids, phenytoin, or bisphosphonates); any medication known to interfere with anastrozole metabolism (tamoxifen and estrogens). 4) diseases known to interfere with bone metabolism as osteoporosis, hyperparathyroidism, untreated hyperthyroidism, osteomalacia, chronic liver disease, renal failure, hypercalcaemia, malabsorption and immobilization; patients with a Total T score lower than -2.0 at Lumbar Spine or Left Femur. 5) symptomatic prostate disease, prostate carcinoma or elevated serum PSA more than 4 ng/ml or >3 for subject with family history of prostate cancer among first degree relatives (needs urologic evaluation before admission into study); 6) hematocrit greater than 50%, untreated severe obstructive sleep apnea, severe lower urinary tract symptoms with International Prostate Symptom Score above 19; 7) documented heart failure, cardiovascular disease, liver disease; 8) excessive alcohol or substance abuse; 9) unstable weight (changes in weight more than ± 2 kg) during the last 3 months; 10) history of bariatric surgery 11) subjects with elevated liver enzymes as alanine transaminase (ALT), aspartate transaminase (AST), alkaline phosphatase (ALP) and bilirubin at more than twice the upper limit of normal.

F2. Procedure

Screening and baseline tests:

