1. Medical, social and medication history, and physical examination, body weight and height will be repeated at 3 and 6 months. DRE will be repeated at 6 months. An additional physical examination (except for digital rectal exam) will be done after 2 weeks from the start of the intervention for safety monitoring. 2. The ADAM quantitative questionnaire, IIEF questionnaire, Stanford physical activity 7 days recall questionnaire, SF-36 questionnaire and the IWQOL will be administered at baseline, 3 and 6 months. 3. Muscle strength by Biodex will be assessed at baseline, 3 and 6 months (not standard of care). 4. Participants will be given instructions for keeping 7-day food intake records and provided with recording forms to estimate energy intake and nutrient composition. The food intake records will be analyzed using the Nutritionist IV computer program (N2 Computing, San Bruno, CA). The Stanford 7-Day Physical Activity Questionnaire will be used to quantify the time spent in different categories of activity during the previous 7 day period. Participants will also be asked to wear accelerometers for the whole intervention and to report daily data concerning the instrument usage. 5. Blood will be collected at 2 weeks a for testosterone, estradiol, LH and FSH, AST, ALT,ALP and bilirubin and at 3 and 6 months for repeat PSA, total testosterone, CBC, CMP, lipid panel, HbA1C, ALP, AST, ALT and bilirubin, markers of bone turnover, estradiol, SHBG, LH, FSH, 25-hydroxy vitamin D and PTH (all test are standard of care except for estradiol and SHBG). 6. Bone mineral density will be measured using DXA, QCT, and HR-pQCT at baseline and 6 months. TBS will be calculated at baseline and 6 months, whereas body composition and visceral adipose tissue volume will be measured at baseline, 3 and 6 months, both will be assessed using DXA. 7. At baseline, 3 and 6 month, blood will be drawn for extraction of DNA, which is part of the cell and os responsible for providing hereditary characteristics. The purpose of analyzing DNA is to determine whether hereditary characteristics are associated with obesity induced HHG and whether the response to weight loss and AI administration is affected by them

Section G: Sample Size/Data AnalysisG1. Sample Size

How many subjects (or specimens, or charts) will be used in this study?

Local: 23 Worldwide: 30

Please indicate why you chose the sample size proposed:

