This is a pilot study with the primary objective of gathering preliminary feasibility and effectiveness data for the development of a bigger study. We plan to enroll 30 subjects for this study. In prior studies of patients with HH using sample sizes of 20-40, a significant increase in T levels was observed for those on AIs compared to those without AIs. In our proposed study, we anticipate a greater increase in T in our patient's randomized to AI over and above the increase resulting from weight loss alone by the same magnitude of increase in above studies which compared the effect of AI alone to those not on AI. Thus, a sample of 30 was chosen for this pilot study. Although the above studies did not include changes in hypogonadal symptoms as outcomes, we anticipate greater improvement in symptoms of hypogonadism among patients on AIs plus weight loss. It is highly likely that we may not be able to find a statistically significant difference between the AIs plus weight loss vs. weight loss alone group in our primary outcomes given this limited sample size, but our results would still provide important information for a bigger study if a trend is observed.

G2. Data Analysis

Provide a description of your plan for data analysis. State the types of comparisons you plan (e.g. comparison of means, comparison of proportions, regressions, analysis of variance). Which is the PRIMARY comparison/analysis? How will the analyses proposed relate to the primary purposes of your study?

Baseline characteristics between groups will be compared using independent t-test or Fisher's exact test. Percent changes in outcomes at 3 and 6-month time points will be compared between the 2 groups using repeated measures analysis of covariance adjusting for covariates such as age, ethnicity and medication use as appropriate. A p value of <0.05 will be considered significant. Simple correlations will be analyzed using Pearson correlation coefficient.

Given the limited sample size, it is possible that we may not find a significant difference in outcomes between the anastrozole+weight loss vs. weight loss alone but the information generated from this pilot study will still be useful if a trend is observed for future proposals or plan for additional recruitment to enhance the sample size.

Section H: Potential Risks/Discomforts H1. Potential Risks/Discomforts

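### G2 does not name each outcome's own baseline value as a covariate, so a chance baseline gap can move the percent-change result and power can be lost

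*Combined protocol and SAP*

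**What the plan says.** Section G2 gives the analysis in one sentence. The comparison is set out first: "Percent changes in outcomes at 3 and 6-month time points will be compared between the 2 groups using repeated measures analysis of covariance". The adjustment is then described by example only: "adjusting for covariates such as age, ethnicity and medication use as appropriate". The words introducing the examples, and the qualifier after them, leave the list open. Baseline adjustment is allowed but not required.

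In the supplied text, an outcome's baseline value otherwise enters the analysis in two ways. It is the divisor of the percent change, and it is part of a between-group check: "Baseline characteristics between groups will be compared using independent t-test". Neither is an adjustment.

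The baseline values will exist. Section F2 (follow-up testing) covers strength in item 3, "Muscle strength by Biodex will be assessed at baseline, 3 and 6 months", and bone density in item 6, "Bone mineral density will be measured using DXA, QCT, and HR-pQCT at baseline and 6 months".

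Sections G1 and G2 accept that significance may not be reached. G2 adds that "the information generated from this pilot study will still be useful if a trend is observed for future proposals". It also mentions recruiting more participants as a possible next step.

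**The concern.** Percent change looks as if it already accounts for where a participant started. In general it does not. Unless follow-up rises with baseline at exactly the rate that the ratio of means implies, percent change remains correlated with baseline. The comparison between arms then carries part of any chance baseline difference, and outcome variance that baseline could explain stays in the error term.

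In a trial of 30, sizeable chance gaps are not rare. The product of this pilot is the size and direction of an estimate, which is to inform a larger study or more recruitment. If that estimate partly reflects which arm started lower, the later decision rests on it. Leaving the covariates to be chosen as appropriate also allows the decision on baseline to be made after the baseline comparisons have been seen.

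**Working it through.** **The plan's own figure.** The sample of 30 (Section G1) cannot be reproduced: no effect size, SD, power or dropout is given. It is used below only as 15 per arm. The 1:1 split is an assumption, because the design attachment named in F1 was not supplied.

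**Assumed inputs.** The documents give no coefficient of variation (CV), baseline-to-follow-up correlation r, or ratio k of follow-up SD to baseline SD.
- Baseline X is normal with mean 100 and SD 20 (CV 20%).
- Follow-up Y has mean 100(1+c), where c is the change common to both arms, SD ratio k and correlation r with X.
- One arm also receives an effect of d × SD(Y).
- There is one follow-up visit, no dropout and a two-sided 0.05 test.
- The outcome is 100(Y−X)/X, analysed with and without X as a covariate.

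**Step 1: how often a gap arises.** The SD of the baseline gap is √(2/15) = 0.365 baseline SDs. So P(|gap| > 0.5 SD) = 2[1 − Φ(0.5/0.365)] = 0.171.

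**Step 2: direction.** To first order, the correlation of percent change with baseline has the sign of k·r − (1+c). With c = 0:
- k = 1, r = 0.5: 0.5 − 1 = −0.5 (negative)
- k = 1.25, r = 0.8: 1.0 − 1 = 0 (none)
- k = 1.5, r = 0.9: 1.35 − 1 = +0.35 (positive)

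The simulated correlations in these three cases were −0.5, 0.00 and +0.49. For testosterone the documents point both ways. Entry requires "low total testosterone (lower than 300 ng/dl) taken from the average of two morning blood samples", which narrows the baseline spread and raises k. G1 expects the drug's effect to come "over and above the increase resulting from weight loss alone", which makes c positive.

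**Step 3: shift from a 0.5 SD gap.** To first order this is 100 × [k·r − (1+c)] × 0.5 × CV percentage points. For k = 1, r = 0.5, c = 0: 100 × (−0.5) × 0.5 × 0.20 = −5.0. Simulated values (c = 0), without baseline in the model:

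| r | k = 1: shift (SE) | k = 1.5: shift (SE) |
|---|---|---|
| 0.5 | −5.8 (8.2) | −3.0 (10.4) |
| 0.7 | −3.5 (6.2) | +0.5 (8.4) |
| 0.8 | −2.3 (5.0) | +2.2 (7.3) |
| 0.9 | −1.2 (3.5) | +4.0 (6.0) |

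With equal SDs this is 5.8/8.2 = 0.7 SE down to 1.2/3.5 = 0.3 SE. With baseline in the model the shift is about 0.

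**Step 4: power (%), without vs with baseline.**

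| Setting | r = 0.5 | r = 0.7 | r = 0.8 | r = 0.9 |
|---|---|---|---|---|
| k = 1, d = 0.8 | 49 vs 62–63 | 70–71 vs 80 | 86 vs 91 | 99 vs 99 |
| k = 1, d = 0.4 | 17 vs 21 | 25 vs 29 | 35 vs 39 | 60 vs 63 |
| k = 1.5, d = 0.8 | 62 vs 64 | 82 vs 81 | 93 vs 92 | 99 vs 99 |
| k = 0.75, d = 0.8 | 35 vs 60 | 50 vs 77 | 63 vs 89 | 82 vs 99 |
| k = 1, c = +20%, d = 0.8 | 40 vs 61 | 58 vs 78 | 73 vs 90 | 92 vs 99 |
| k = 1.5, c = +20%, d = 0.8 | 58 vs 64 | 79 vs 80 | 92 vs 92 | 99.7 vs 99.6 |

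A 48-cell grid was run over k = 0.75 to 1.5, c = −10, 0 and +20%, and r = 0.5 to 0.9. At d = 0.8 the gain runs from −1.3 to +40 points (median 5). At d = 0.4 it runs from −1.3 to +34 (median 3). It is under 1 point in 18 of the 48 cells at each effect size. The cells are not weighted by plausibility.

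**Step 5: type I error.** Overall it is 4.8–5.0% in every cell for both analyses. Given a gap above 0.5 SD, without baseline and with c = 0, it is about 12, 9, 8 and 7% (k = 1) and 6, 5, 6 and 11% (k = 1.5) for r = 0.5, 0.7, 0.8 and 0.9. The largest value is 23% (k = 0.75, c = +20%). With baseline it is 4.3–5.1% in every cell.

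**Step 6: two checks.** Using the mean of the 3- and 6-month values (d = 0.8; r = 0.5, 0.7, 0.9), power is 59 vs 79, 81 vs 91 and 99.7 vs 99.9% with equal SDs. With k = 1.5 it is 78 vs 82, 93 vs 92 and 99.8 vs 99.9%. A lognormal version with equal SDs (CV 0.15 and 0.30, r = 0.3 to 0.9, effect of 1 SD of change) gave gains of about 0 to 16 points at N = 30 and 0 to 15 at N = 23.

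**The case against.** The strongest reply is that this is an ambiguity and not an error. The covariate list is illustrative, so an analyst may include baseline, and every harm above applies only if it is left out. Randomisation keeps the unadjusted comparison free of bias on average and its overall type I error near 5%. The raised type I figures are conditional on a gap that occurs in about one trial in six, and with equal SDs a 0.5 SD gap moves the estimate by less than one standard error. The largest gains need an outcome whose mean rises while its spread shrinks, which nothing in the documents suggests. For testosterone, the one outcome with any anchor in the text, the nearest row (k = 1.5, c = +20%) shows a gain of about 0 to 6 points. This is a pilot that already expects to miss significance.

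All of that stands as a limit on size. It does not remove the point. The freedom to include baseline is also freedom to omit it, or to decide after seeing the baseline tests. The pilot's estimate is meant to steer a larger study, and G2 still sets p < 0.05 as its criterion.

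A further objection is that the main calculation has no other covariates, so the cost of one more in a small model is untested. With four extra covariates in the model, the largest power loss from adding baseline was about 1.5 points. Closing the list of the remaining covariates is ordinary prespecification, and the finding does not depend on it.

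**Conclusion.** The concern holds. That G2 does not name the outcome's baseline value is certain from the supplied text. The consequence is conditional on its being left out: no loss of overall validity, but an estimate that can move with chance imbalance and a possible loss of power. The loss ranges from nil to large, with a median of 3 to 5 points over the unweighted grid, and the direction of the shift cannot be known in advance. Confidence in the size is only medium, because the correlation, CV, SD ratio, effect size and 1:1 allocation are all assumed. The recommendation does not depend on knowing them: including baseline removed the dependence in every case run and never cost more than about 1 to 1.5 points of power. It should be fixed, but it is not fatal.

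**What to change.** Replace the open covariate wording in G2 with a sentence such as:

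> Each outcome's baseline value will be a fixed covariate in its model; any further covariates are listed here and fixed before the data are analysed by group.

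Percent change can remain the outcome. Analysing the follow-up values themselves (on the log scale for hormones), with percent change shown descriptively, is an option but is not needed to resolve this point.

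The cost is a change of wording and one model degree of freedom. No new measurements are required, since the baseline values are already collected under F2.

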1. Medical, social and medication history, body weight and height data will be collected and a physical examination with a digital rectal examination (DRE) will be done (all are standard of care). 2. Blood testing will be obtained for fasting testosterone from two samples taken between 8-11 AM at 2 separate days and at least 2-3 days apart (standard of care). 3. Blood tests for comprehensive metabolic panel (CMP), fasting lipid panel, aspartate aminotransferase (AST), alanine aminotransferase (ALT), alkaline phosphatase (ALP), bilirubine, HbA1c, complete blood count (CBC), prostate specific antigen (PSA), luteinizing hormone (LH), follicle stimulating hormone (FSH), prolactin, thyroid stimulating hormone (TSH), insulin growth factor-1 (IGF1), free thyroxine (FT4), cortisol, adrenocorticotropic hormone (ACTH), 25-hydroxyvitamin D (25OHD), parathyroid hormone (PTH), estradiol, bone markers osteocalcin, and N-terminal telopeptide (NTx), and sex hormone binding globulin (SHBG). Blood obtained from an antecubital vein, will be processed immediately, and be stored in aliquots at -80C (standard of care). 4. Quantitative Androgen Deficiency in Aging Male (ADAM) questionnaire to assess for symptoms of hypogonadism and severity (25), International Index of Erectile Function (IIEF) questionnaire, Stanford physical activity 7 days recall questionnaire, SF-36 questionnaire to assess patient's quality of life, and the Impact of Weight on Quality of Life Questionnaire- Lite (IWQOL) to evaluate the effect of excess weight on quality of life will be all administered. These questionnaires are mostly research although most of the questions in the questionnaires are part of the review of systems which is standard of care. 5. Muscle strength will be

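### Percent change is the only outcome scale in G2, so questionnaire results will depend on a scoring origin and direction that the plan does not define

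*Combined protocol and SAP*

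**What the plan says.** Section G2 (Data Analysis) describes one between-group analysis of outcomes: "Percent changes in outcomes at 3 and 6-month time points will be compared between the 2 groups". The model is a repeated-measures ANCOVA with an open list of covariates, in which the baseline value of the outcome is not named. The significance rule is "A p value of <0.05 will be considered significant". The word for outcomes is unqualified, and no absolute change, transformation or rule for a zero baseline is given.

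Section D puts hypogonadal symptoms in Objective 1, beside muscle strength. F2, Screening and baseline tests, item 4, lists the "Quantitative Androgen Deficiency in Aging Male (ADAM) questionnaire to assess for symptoms of hypogonadism and severity (25), International Index of Erectile Function (IIEF) questionnaire", followed by the SF-36 for quality of life and the IWQOL for weight-related quality of life. F2, Follow-up testing, item 2, schedules all four at the time points that G2 analyses; for the last two it says "SF-36 questionnaire and the IWQOL will be administered at baseline, 3 and 6 months". The text gives no score range, zero point, scoring version or direction of benefit for any of them. Eligibility in F1 is biochemical and anthropometric and sets no limit on baseline ADAM, IIEF, SF-36 or IWQOL scores.

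G1 says of the primary outcomes: "It is highly likely that we may not be able to find a statistically significant difference". Both G1 and G2 place the value of the pilot in whatever trend is seen.

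**The concern.** A percentage of baseline has a fixed meaning only where zero means none of the quantity. Peak torque in newton-metres and BMD qualify. A questionnaire total does not: its lowest value and its direction are conventions of the scoring manual. Change in points is unaffected when the origin is moved, and reversing the scale only flips its sign. Percent change is altered by both.

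Under G2 as written, the same answers from the same men can therefore give a different size of group difference, and a different weighting of the men, according to a scoring choice that the plan leaves open. If scores come close to zero, individual values can become very large or undefined. A pilot that expects no significant result has the size of its estimates as its main product, so this affects what the larger study would be planned on.

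**Working it through.** **1. The plan's own figure.** G1 states "We plan to enroll 30 subjects for this study" with no effect size, SD or power, so 30 cannot be reproduced. For scale, assume 15 per arm (the allocation ratio is not in the supplied text) and two-sided 0.05. The difference detectable with 80% power is (1.960 + 0.842) × √(2/15) = 1.02 SD. There is little power to spare.

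**2. Arithmetic on origin and direction.** Take a gain of 5 points from baseline b. The percent change is 100 × 5/b on the score as it stands, 100 × 5/(b + 10) if the scale starts 10 points higher, and 100 × (−5)/(50 − b) if the score is reversed on an assumed maximum of 50.

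| Baseline b | As scored | Origin moved by 10 | Reversed | Change in points |
|---|---|---|---|---|
| 5 | +100% | +33% | −11% | 5 |
| 10 | +50% | +25% | −12.5% | 5 |
| 20 | +25% | +17% | −17% | 5 |
| 40 | +12.5% | +10% | −50% | 5 |

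In an arm of 15, the first man adds 100/15 = 6.7 percentage points to the arm mean and the last adds 12.5/15 = 0.8, for the same gain. Reversing the score swaps which of them counts most. This step needs no assumption about any particular instrument.

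**3. Simulation of the cost.** Inputs, all assumed: 15 per arm, baseline to follow-up correlation 0.6, true effect 0.8 SD, one follow-up visit, integer scores, no covariates other than baseline where shown, and 8,000 trials per run. Men with a baseline of zero drop out of the percent-change analysis. Ranges span repeat runs.

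| Assumed baseline: mean, SD, range | Power, points | Power, percent | Points, baseline-adjusted | Percent, baseline-adjusted | Trials with a zero baseline |
|---|---|---|---|---|---|
| 30, 6, 10–50 | 0.65 | 0.58 | 0.73 | 0.69–0.70 | 0% |
| 30, 10, 0–75 | 0.65–0.66 | 0.43–0.44 | 0.73–0.74 | 0.55–0.56 | 5% |
| 30, 15, 0–75 | 0.65–0.66 | 0.30–0.31 | 0.72–0.74 | 0.38–0.39 | 52–53% |
| 15, 10, 0–75 | 0.65–0.67 | 0.27–0.28 | 0.73 | 0.34–0.35 | 90% |

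Comparing like with like, the loss comes from the percentage scale. Adding baseline as a covariate raises power on both scales but does not close the gap.

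The p<0.05 verdict on percent change also depended on scoring. Across the four rows, moving the origin by 10 points changed it in about 3%, 11%, 22% and 31% of trials. Reversing the score changed it in about 16–20%, 28%, 39% and 42%. In the first row the lower figure reverses the score within its own range of 10 to 50; the higher one uses 51 minus the score.

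The loss of power is not uniform. On the reversed scores, percent change had power of 0.57 to 0.66, close to change in points in several rows, because the baselines then sat further from zero.

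With no true effect, percent change rejected in 0.03 to 0.05 of trials.

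**The case against.** The strongest reply is that both arms share one scoring and one metric, so the comparison stays valid. The simulated type I error supports this: a reader might infer that the between-group test is biased towards false positives, and it is not.

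Second, the plan gives no score range, floor or baseline distribution. A reader might infer that the symptom result will hang on a few men with low scores, or that the most symptomatic men will be lost or will dominate. Neither is established. In the first assumed distribution no zero baseline occurs, a shift of origin changes the verdict in only 3% of trials, and the gain from using points is only 0.58 to 0.65. Small denominators belong to the most symptomatic men only where a low score is the bad end; where a high score is worse, those men show the smallest percentages.

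Third, it is tempting to say that all four questionnaires carry Objective 1. F2 gives the symptom task to the ADAM alone. The SF-36 and IWQOL measure quality of life, which is in none of the three objectives. The IIEF is given no stated role in F2, although Section I counts sexual function among hypogonadal symptoms.

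Fourth, G2 is a brief form entry and cannot govern every outcome literally, since F2 measures BMD only at baseline and 6 months. The design attachment named in F1 is also not available. This is fair, but G2 is where the analysis plan is stated, it names no other scale, and the questionnaires are collected at exactly its time points.

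Finally, this is a pilot that does not expect significance. That limits the weight of the power figures. It does not protect the size of the trend, which is what the pilot hands on.

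**Conclusion.** The concern holds in limited form. G2 states percent change as its only outcome scale, and this covers the quantitative ADAM (the Objective 1 symptom measure) and the IIEF, SF-36 and IWQOL. That percent change on such scores depends on origin and direction is arithmetic and needs no assumption; the supplied text defines neither.

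The size of the cost does rest on assumptions. With 15 per arm, correlation 0.6 and a true effect of 0.8 SD, percent change had power from about 0.58 down to about 0.28, against 0.65 to 0.67 for change in points, without baseline adjustment in either. The loss is modest if scores sit well above zero and large if they approach it. Undefined values and dominance by a few men are possible consequences, not demonstrated ones.

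The harm is to the precision and interpretability of the symptom trend. Percent change remains reasonable for physical measures with a true zero. The change is worth making because it is cheap and can be fixed before any scores are compared.

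**What to change.** In G2, state that the ADAM, IIEF, SF-36 and IWQOL will be compared between groups as change in points on the published score, in the same repeated-measures model, with the baseline score added as a covariate. For each instrument, name the scoring version and say which direction is benefit. Percent change may stay for physical measures with a true zero, such as peak torque and BMD.

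This costs a sentence or two in G2 and needs no new data, visits or participants. The small downside is that questionnaire and physical outcomes will no longer share one unit in the results tables.
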